^s A pre-treatment tumor tissue sample will be analyzed for ASPH expression. After signing of the Informed Consent Form, tumor tissue should be submitted to the Sponsor in a timely manner. A pre-treatment sample is defined as a specimen obtained after initiation of ongoing CPI therapy and before first dose of SNS-301 and pembrolizumab on this current clinical trial. Patients are requested to provide archival tissue from a prior biopsy or surgery that is treatment -naïve including prior 1) chemotherapy, radiation and/or 2) anti-PD(L)-1 treatment-naïve, pending availability. Tumor tissue should be of good quality based on total and viable tumor content. Acceptable samples include core needle biopsies for deep tumor tissue or lymph nodes or excisional, incisional, punch, or forceps biopsies for cutaneous, subcutaneous, or mucosal lesions. Fine-needle aspiration may be acceptable pending Sponsor approval however, brushing, cell pellets from pleural effusion, and lavage samples are not acceptable. For core needle biopsy specimens, at least three cores should be submitted for evaluation. The patient may start study treatment prior to receiving the ASPH expression results from the fresh biopsy or archival tissue from a previous biopsy. All patients will undergo a mandatory tumor biopsy sample collection, if clinically feasible as determined by the trial investigator, at the Week 6 (at the time of third dose ± 3 days). Additionally, up to two optional biopsies may be obtained at any time during the study, if medically feasible. A biopsy may also be obtained at the first evidence of radiographic or clinical disease progression (i.e., not proceeded by meaningful tumor regression). For patients who respond and subsequently progress, an optional biopsy may be obtained at the time of disease progression. Patients who are unable to undergo biopsy sample collection but otherwise meet criteria outlined in protocol may continue to receive study treatment. If the patient is unable to have the biopsy at the protocol specified visit (i.e., COVID19 related) then an unscheduled biopsy may be performed.

^t AEs will be collected from the time of informed consent until 30 days after the last dose of study treatment or until initiation of another anti-cancer therapy, whichever occurs first. SAEs and AESIs will be collected from the time of informed consent until 90 days after the last dose of study treatment or until initiation of anti-cancer therapy, whichever occurs first.

^u Pembrolizumab will be given every 3 weeks until confirmed disease progression, unacceptable toxicity, deemed intolerable by investigator or up to 24 months in patients without disease progression. The window for each visit is ± 3 days unless otherwise noted. A 60 minutes observation period is recommended for the first dose and 30 minutes for subsequent doses.

^v SNS-301 is administered every 3 weeks until week 9 (i.e., 4 doses). Then every 6 weeks for 6 more doses (until week 45). Thereafter it will be administered every 12 weeks until confirmed disease progression, unacceptable toxicity, deemed intolerable by investigator or up to 24 months in patients without disease progression. The window for each visit is ± 3 days unless otherwise noted. A 30-minute observation period is recommended after each study treatment.

^w Survival follow-up information will be collected via telephone calls, patient medical records, and/or clinical visits approximately every 3 months for up to 3 years, until death, lost to follow-up, withdrawal of consent, or trial termination by Sponsor. All patients will be followed for survival and new anticancer therapy information unless the patient requests to be withdrawn from follow-up; this request must be documented in the source documents and signed by the investigator. If the patient discontinues study treatment without documented clinical disease progression, every effort should be made to follow up regarding survival, progression (, and new anti-cancer therapy.

Pembrolizumab Schedule – Every 6 weeks

	Screening ^a	Cycle 1 Day 0	Cycle 2 Week 3	Cycle 3 Week 6	Cycle 4 Week 9	Every 6 weeks	Every 12 weeks	Discontinuation Visit ^b	Follow-up
	Day -28 to Day -1								
Signed Informed Consent Form(s)	X								
Medical, surgical, and cancer histories, including demographic information^c	X								
Inclusion/Exclusion criteria	X	X							
Complete Physical exam^d	X								
Targeted Physical exam^e		X ^f	X ^f	X ^f	X ^f	X ^f		X	
ECOG performance status^f	X	X	X	X	X	X		X	
HIV, Hep B and Hep C serology^g	X								
Concomitant Medications^h	X	X	X	X	X	X		X	
Anticoagulant specific drug and/or anticoagulant factor Xa levelsⁱ	X	X	X	X	X	After week 12, Q6w until week 42, thereafter Q12w			X
For patients on anticoagulants only									
Vital Signs and Weight^j	X	X	X	X	X	X		X	
Height	X								
12-lead ECG^k	X								
Tumor Imaging^l	X	Q6w from Day 0 until ~12 months, there after Q12w							
RECIST/iRECIST	X	Q6w from Day 0 until ~12 months, there after Q12w							
Hematology^m	X	X ^f	X ^f	X ^f	X ^f	X ^f		X	
Serum Chemistryⁿ	X	X ^f	X ^f	X ^f	X ^f	X ^f		X	
Coagulation Panel (aPTT, INR)	X								
Urinalysis^o	X			X		X		X	
Pregnancy^p	X	X	X	X	X	X		X	X
TSH, T3 and Free T4^q	X			X		X			
CPK	X							X	
HPV/EBV, if unknown	X								
PDL-1	X								
Blood samples for immunology assessments^r		X	X	X	X	At week 12, then Q6 weeks until Week 36 and Q12w thereafter as well as at disease progression			
Tumor specimens^s	X			X		Up to 2 optional biopsies and at disease progression			
Adverse Events^t	X	X	X	X	X	X		X	X
Pembrolizumab^u		X		X		X			

SNS-301 ^v		X	X	X	X	After week 12, Q6w for 6 more doses (week 45), thereafter Q12w until PD or 24 months if no PD		
Survival and new anti-cancer therapy follow-up ^w								X

Note: Assessments scheduled on the days of study treatment should be performed before the study treatment unless otherwise noted.

^a Written informed consent can be obtained up to 28 days prior to Day 0 and is required for performing any trial-specific tests or procedures. However, tumor tissue collection (archived or fresh) can exceed 28 days to ensure that sufficient time is available for obtaining the requested sample for trial purposes. Additionally, a pre-screening informed consent is available to obtain archived tumor tissue prior to the study's primary consent. Results of standard-of-care tests or examinations performed prior to obtaining informed consent and within 28 days prior to Day 0 may be used for screening assessments rather than repeating such tests. Screening labs (CBC and chemistry) may be used for Day 0 if they are within 10 days of Day 0.

^b Patients who discontinue early from study treatment (i.e., progression, adverse event, etc.), will be asked to return to the clinic within 30 days after the last dose for a treatment discontinuation visit.

^c Cancer history includes stage, date of diagnosis, and prior anti-tumor treatment. Previous progression data should be collected as well. Demographic information includes sex, age, and self-reported race/ethnicity. HPV, EBV, reproductive status and smoking/alcohol history should also be captured.

^d A complete physical exam will include head, eyes, ears, nose, throat and cardiovascular, dermatological, musculoskeletal, respiratory, gastrointestinal and neurological systems. Height and weight will also be collected. Any signs and symptoms, other than those associated with a definitive diagnosis, should be collected at baseline and during the study.

^e A targeted, symptom-directed exam will be performed, as clinically indicated.

^f ECOG performance status, targeted physical exam, and local laboratory assessments may be obtained \leq 72 hours before each dosing visit.

^g Patients should be tested for HIV locally prior to the inclusion into the trial only based on investigator's clinical suspicion for HIV infection and HIV-positive patients will be excluded from the clinical trial. Hepatitis B surface antigen, anti-HBc antibody, anti-HBs antibody, and Hepatitis C antibody immunoassays should be tested only per investigator's clinical suspicion during screening and tested locally. In patients who have positive serology for the anti-HBc antibody, HBV DNA should be tested prior to Day 0.

^h Concomitant medications include any prescription medications or over-the-counter medications. At screening, any medications the patient has used within the 7 days prior to the screening visit should be documented. At subsequent visits, changes to current medications or medications used since the last documentation of medications will be recorded.

ⁱ Specific anticoagulant drug and/or anticoagulant factor Xa levels will be obtained only on patients receiving anticoagulant therapy. Drug levels will also be obtained at any time of clinical bleeding. Traditional testing methods can be used for warfarin, heparin (e.g., PT/INR, aPTT, TT). Novel oral anticoagulants may require anticoagulant factor Xa levels or anticoagulant drug specific level testing. See sections Concomitant Medications & Guidance for Investigators for Patients on Anti-coagulants for additional information.

^j Vital signs include heart rate, respiratory rate, blood pressure, and temperature. For first infusion of pembrolizumab, the patient's vital signs should be determined within 60 minutes before the start of the infusion. If clinically indicated, vital signs should be at 15, 30, 45, and 60 minutes (\pm 5 minutes for all timepoints) after the start of the infusion, and 30 (\pm 10) minutes after the infusion. For subsequent infusions, vital signs will be collected within 60 minutes before the start of the infusion and at 30 (\pm 5) minutes after the infusion. Patients will be informed about the possibility of delayed post-infusion symptoms and instructed to contact their trial physician if they develop such symptoms.

^k ECG recordings will be obtained during screening and as clinically indicated at other time points. Patients should be resting and in a supine position for at least 10 minutes prior to ECG collection.

^l Examinations performed as standard of care prior to obtaining informed consent and within 28 days of first dose of study treatment may be used rather than repeating tests. All measurable and evaluable lesions should be assessed and documented at the screening visit. Tumor imaging should be performed by computed tomography (CT), but may be performed by magnetic resonance imaging (MRI) if CT is contraindicated, but the same imaging technique should be used in patient throughout the trial. CT scans (with oral/IV contrast unless contraindicated) must include chest, abdomen and pelvis. The investigator must review before dosing at the next visit. Patients will undergo tumor assessments every 6 weeks (\pm 7 days) for the first approximately 12 months following first dose of study treatment, or earlier if clinically indicated. After approximately one year, tumor assessments will be required every 12 weeks (\pm 7 days). Patients who discontinue from treatment for reasons other than disease progression (e.g., toxicity) will continue

scheduled tumor assessments until disease progression, start of new-anti cancer therapy, withdrawal of consent, or death. Investigators may perform additional scans or more frequent assessments if clinically indicated. Patients who continue treatment beyond radiographic or clinical disease progression will be monitored with a follow-up scan at the next scheduled tumor assessment. Imaging timing should follow calendar days and should not be adjusted for delays or changes in treatment administration dates. The Sponsor may request digitized scans from patients during the study.

^m Hematology consists of CBC, including RBC count, hemoglobin, hematocrit, WBC count with automated differential (absolute counts of neutrophils, lymphocytes, eosinophils, monocytes, basophils, and other cells (if any)), and platelet count. A manual differential can be done if clinically indicated.

ⁿ Serum chemistry includes BUN or urea, creatinine, sodium, potassium, magnesium, chloride, bicarbonate or CO₂, calcium, phosphorus, glucose, total bilirubin (direct bilirubin only if total bilirubin is elevated), ALT, AST, alkaline phosphatase, lactate dehydrogenase, total protein, and albumin.

^o Urinalysis includes specific gravity, pH, glucose, protein, ketones, blood, and a microscopic exam if abnormal results are noted. Urinalysis to be performed every 6 weeks.

^p Serum pregnancy test (for women of childbearing potential, including women who have had a tubal ligation) must be performed and documented as negative within 72 hours prior to each dose.

^q Thyroid function tests will be performed before first dose and every 6 weeks thereafter.

^r Immunology samples are to be drawn at Day 0, Week 3, Week 6, Week 9, 12, then Q6 weeks until Week 36 and thereafter every 12 weeks until disease progression, as well as at disease progression.

^s A pre-treatment tumor tissue sample will be analyzed for ASPH expression. After signing of the Informed Consent Form, tumor tissue should be submitted to the Sponsor in a timely manner. A pre-treatment sample is defined as a specimen obtained after initiation of ongoing pembrolizumab, nivolumab or other CPI therapy and before first dose of SNS-301 and pembrolizumab on this current clinical trial. Patients are requested to provide archival tissue from a prior biopsy or surgery that is treatment –naïve including prior 1) chemotherapy, radiation and/or 2) anti-PD(L)-1 treatment-naïve, pending availability. Tumor tissue should be of good quality based on total and viable tumor content. Acceptable samples include core needle biopsies for deep tumor tissue or lymph nodes or excisional, incisional, punch, or forceps biopsies for cutaneous, subcutaneous, or mucosal lesions. Fine-needle aspiration may be acceptable pending Sponsor approval however, brushing, cell pellets from pleural effusion, and lavage samples are not acceptable. For core needle biopsy specimens, at least three cores should be submitted for evaluation. The patient may start study treatment prior to receiving the ASPH expression results from the fresh biopsy or archival tissue from a previous biopsy. All patients will undergo a mandatory tumor biopsy sample collection, if clinically feasible as determined by the trial investigator, at the Week 6 (at the time of third dose of SNS-301 +/- 3 days). Additionally, up to two optional biopsies may be obtained any time during the study, if medically feasible. A biopsy may also be obtained at the first evidence of radiographic or clinical disease progression (i.e., not proceeded by meaningful tumor regression). For patients who respond and subsequently progress, an optional biopsy may be obtained at the time of disease progression. Patients who are unable to undergo biopsy sample collection but otherwise meet criteria outlined in protocol may continue to receive study treatment. If the patient is unable to have the biopsy at the protocol specified visit (i.e., COVID19 related) then an unscheduled biopsy may be performed.

[figure not shown]
^t AEs will be collected from the time of informed consent until 30 days after the last dose of study treatment or until initiation of another anti-cancer therapy, whichever occurs first. SAEs and AESIs will be collected from the time of informed consent until 90 days after the last dose of study treatment or until initiation of anti-cancer therapy, whichever occurs first.

^u Pembrolizumab will be given every 6 weeks until confirmed disease progression, unacceptable toxicity, deemed intolerable by investigator or up to 24 months in patients without disease progression. **After week 9, the pembrolizumab and SNS-301 visits will not coincide. The SNS-301 dosing should not be adjusted. The investigator may choose to give a 3-week dose (i.e., pembrolizumab 200 mg) in order for the visits to align. The investigator should consult the sponsor if there are questions regarding aligning the study treatment schedule.** The window for each visit is \pm 3 days unless otherwise noted. A 60 minute observation period is recommended for the first dose and 30 minutes for subsequent doses.

^v SNS-301 is administered Day 0, Week 3, Week 6 and Week 9, then every 6 weeks for 6 more doses (until week 48). Thereafter it will be administered every 12 weeks until confirmed disease progression, unacceptable toxicity, deemed intolerable by investigator or up to 24 months in patients without disease progression. The window for each visit is \pm 3 days unless otherwise noted. A 30-minute observation period is recommended after each study treatment.

^w Survival follow-up information will be collected via telephone calls, patient medical records, and/or clinical visits approximately every 3 months for up to 3 years, until death, lost to follow-up, withdrawal of consent, or trial termination by Sponsor. All patients will be followed for survival and new anticancer therapy information unless the patient requests to be withdrawn from follow-up; this request must be documented in the source documents and signed by the investigator. If the patient discontinues study treatment without documented clinical disease progression, every effort should be made to follow up regarding survival, progression and new anti-cancer therapy.

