10. Patients who discontinue from study treatment for reasons other than disease progression (e.g., toxicity) will continue scheduled tumor assessment until disease progression, withdrawal of consent, or start of new anti-cancer therapy, death, or trial termination by Sponsor, whichever occurs first.

Safety Run-In: A safety run-in will be performed using a modified rolling six design which will enroll up to six patients (safety lead-in patients). A Safety Committee will review data from the Safety Run-In. (Refer to Section [Safety Committee](#)).

Once the first three patients of these six patients have completed Week 6 assessments, in the absence of any dose-limiting toxicity (DLT), enrollment may proceed through stage 1. However, if prior to the first three patients completing Week 6, a single patient from the first six experiences a DLT, then enrollment will be

limited to six patients until all six patients have reached Week 6 and are assessed for DLT. If no additional patients, of these six, experience a DLT within the 6-week safety run in period, then enrollment may proceed to completion.

If a second of these first six patients experiences a DLT within the first six weeks, enrollment will stop, and the Sponsor's medical monitor, in addition to the PI and Investigator(s) at the patients' site(s) will discuss the case, and a decision will be made whether to modify the trial or to cease further enrollment. If enrollment is ceased, it will only be reinitiated after amendment of the protocol and approval of the amended protocol by the IRB.

Safety run-in patients that withdraw from the study for reasons other than a DLT, prior to the end of the safety run-in period, will be replaced. The end of the safety run-in period is defined as the earliest of the following:

- The first three patients in cohort A have all completed Week 6 with no DLTs experienced by any of the safety run-in patients in that cohort (up to six); enrollment may then proceed to completion;
- All six patients of the safety run-in phase, in cohort A, have completed week six with only one patient having experienced a DLT; enrollment may then proceed to completion;
- Two or more of the safety run-in patients, have experienced DLTs prior to completing Week 6; enrollment will be suspended.

Dose-Limiting Toxicities (DLTs) are defined in protocol

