This study will employ a Simon 2-stage design, with 15 evaluable patients (i.e. meeting the definition for the efficacy evaluable analysis set; at Week 12 for both cohorts). The criteria for advancing to Stage 2 is described in Section 10.2. Non-evaluable patients will be replaced.

The safety run-in will be performed using a modified rolling six design which will enroll up to six patients (safety analysis patients). These patients may contribute to the first 15 in stage 1, assuming they meet the definition for evaluable for efficacy.

Once the first three patients of these six patients have completed Week 6 assessments, in the absence of any dose-limiting toxicity (DLT), enrollment may proceed through stage 1. However, if prior to the first three patients completing Week 6, a single patient from the first six experiences a DLT, then enrollment will be limited to six patients until all six patients have reached Week 6 and are assessed for DLT. If no additional patients, of these six, experience a DLT within the 6-week safety run in period, then enrollment may proceed to completion.

If a second of these first six patients experiences a DLT within the first six weeks, enrollment will stop, and the Sponsor's medical monitor, in addition to the PI and Investigator(s) at the patients' site(s) will discuss the case, and a decision will be made whether to modify the trial or to cease further enrollment. If enrollment is ceased, it will only be reinitiated after amendment of the protocol and approval of the amended protocol by the IRB.

Safety run-in patients that withdraw from the study for reasons other than a DLT, prior to the end of the safety run-in period, will be replaced. The end of the safety run-in period is defined as the earliest of the following:

- The first three patients have all completed Week 6 with no DLTs experienced by any of the safety run-in patients in that cohort (up to six); enrollment may then proceed through stage 1;
- All six patients of the safety run-in phase, have completed week six with only one patient having experienced a DLT; enrollment may then proceed through stage 1;
- Two or more of the safety run-in patients, have experienced DLTs prior to completing Week 6; enrollment will be suspended.

DLTs are defined in the protocol section 9.3.9.

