10.2 Sample Size Determination

Adverse events will be continuously monitored. Among the first phase of 15 patients, for adverse events that occur at an incidence of 18% the probability of observing at least one event is approximately 95%. Among all 60 patients, for adverse events that occur at an incidence of 5% the probability of observing at least one event is approximately 95%.

The sample size for each cohort and stage is based on Simon's two-stage design for tests of one proportion.

Cohort A

To evaluate the primary endpoint of objective response rate per iRECIST at 12 weeks with a null hypothesis of an objective response rate (ORR) of 5% and an alternative hypothesis of an ORR of 18%, 30 patients in a two-stage design with 15 patients in the first stage and 15 patients in the second stage will be enrolled. At the first stage analysis if at least 1 response is observed out of 15 patients, the study will continue through the second stage. At the second stage analysis, if at least 4 responses are observed out of 30 total patients, the null hypothesis will be rejected and further research considered warranted. The overall power for objective response rate at 12 weeks is 80%. The overall type I error, the chance of incorrectly rejecting the null hypothesis is 6% (targeted alpha of 0.10). The probability of stopping at the first stage under the null hypothesis is 46%. The operating characteristics of this design are calculated using the exact binomial distribution.

Cohort B

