Version 1.0

Sponsor: Sensi Biotherapeutics

Protocol: SNS301-2-2

This study will employ a Simon 2-stage design, with 15 evaluable patients (i.e. meeting the definition for the efficacy evaluable analysis set; at Week 12 for both cohorts. Non-evaluable patients will be replaced.

The safety run-in will be performed using a modified rolling six design which will enroll up to six patients (safety analysis patients). These patients may contribute to the first 15 in stage 1, assuming they meet the definition for evaluable for efficacy. The end of the safety run-in period is defined as the earliest of the following:

- The first three patients have all completed Week 6 with no DLTs experienced by any of the safety runin patients in that cohort (up to six); enrollment may then proceed through stage 1;
- All six patients of the safety run-in phase, have completed week six with only one patient having experienced a DLT; enrollment may then proceed through stage 1;
- Two or more of the safety run-in patients, have experienced DLTs prior to completing Week 6; enrollment will be suspended.

If at least one responder (ORR per iRECIST) is observed in the first 15 evaluable patients (i.e. meeting the definition for the efficacy evaluable population) by Week 12, then the study will continue to Stage 2 and enroll up to 15 additional patients. If at least 4 responders are observed overall, further research will be deemed warranted.

[figure not shown]
There will be a waiting period of one week between enrollment of the first patient and the second patient because this trial is treating patients with SNS-301 and pembrolizumab for the first time. The interim efficacy assessment, for each cohort, will occur after 15 patients were enrolled and completed the 12-week follow-up period. A safety review will occur in parallel to the efficacy assessment of the first 15 patients

The trial will be stopped if any adverse experience of any related death, grade 4 autoimmune toxicity or any grade 4 toxicity that is considered to have a causal relationship to study drug should occur. These events will be submitted to regulatory agencies within the expedited safety reporting criteria.

The clinical trial will be considered completed when all patients have had their three-year follow-up visit, death, lost to follow-up, withdrawal of consent, or when the Sponsor deems the study completed, whichever comes first.

The study schema is presented in Figure 1:

Figure 1: Study Schema

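### Clearing the safety run-in opens enrolment to completion in four places and only through stage 1 elsewhere; acting on the completion text would bypass the stage 2 response gate

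*Protocol*

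**What the plan says.** The protocol synopsis (Section 1.1, Safety Run-In) and Section 5.2 each describe the run-in twice: in a narrative paragraph and in bullets that define its end.

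- **Synopsis, paragraph.** If the first three patients finish Week 6 without a DLT: "in the absence of any dose-limiting toxicity (DLT), enrollment may proceed through stage 1". If there is one DLT among the six and no second, the paragraph switches to completion.
- **Synopsis, bullets.** For no DLT: "in that cohort (up to six); enrollment may then proceed to completion". The one-DLT bullet also says completion. Both bullets name Cohort A.
- **Section 5.2, paragraph.** The no-DLT sentence stops at stage 1. The one-DLT sentence reads "experience a DLT within the 6-week safety run in period, then enrollment may proceed to completion".
- **Section 5.2, bullets.** Both stop at stage 1; the no-DLT bullet reads "in that cohort (up to six); enrollment may then proceed through stage 1".
- **SAP 2.2, bullets.** Both stop at stage 1; the one-DLT bullet reads "having experienced a DLT; enrollment may then proceed through stage 1".

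Stage 2 has its own condition elsewhere. The synopsis makes the second 15 patients depend on response. Section 5.2 sends the reader to Section 10.2 for the criteria. Section 10.2 requires at least 1 response in 15 (Cohort A) or at least 2 in 15 (Cohort B). Section 10.5 places the response assessment at the end of stage 1, and SAP 2.2, 2.4 and 9.5 repeat the scheme. For Cohort A, Section 10.2 states: "The probability of stopping at the first stage under the null hypothesis is 46"%. For Cohort B it gives 38.8%.

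**The concern.** For the same event, a site can find two different enrolment limits in operative text. The run-in clears when three to six patients have reached Week 6. The stage 1 decision needs 15 evaluable patients at Week 12. A permission to enrol to completion at the first point therefore cannot be followed literally while the second is respected.

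Two features make the wrong reading easier. The synopsis gives no response threshold and refers to Section 10 instead. Section 7.1.2.3 allows further enrolment after clearance without naming a stage. The sections on the interim look say when it happens but do not say in terms that accrual waits for it.

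At stake are patients enrolled after their cohort has already met its futility criterion, and early-stopping probabilities that would no longer describe the trial as run.

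**Working it through.** **Step 1. Set the wordings side by side.**

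| Place | No DLT | One DLT in six |
|---|---|---|
| Synopsis, paragraph | stage 1 | completion |
| Synopsis, bullets | completion | completion |
| Section 5.2, paragraph | stage 1 | completion |
| Section 5.2, bullets | stage 1 | stage 1 |
| SAP 2.2, bullets | stage 1 | stage 1 |

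The synopsis contradicts itself on the no-DLT event, and Section 5.2 contradicts itself on the one-DLT event. There are four completion phrases, and three of them apply only after one DLT.

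**Step 2. Reproduce the stated design.** Inputs from Section 10.2: n1 = 15 and n = 30 in each cohort. Cohort A: p0 = 0.05, p1 = 0.18, continue with at least 1 response, reject the null with at least 4. Cohort B: p0 = 0.133, p1 = 0.29, continue with at least 2, reject with at least 7.

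Probability of stopping at stage 1 under the null:
- A: P(X1 = 0) = 0.95^15 = 0.463 (stated 46%).
- B: P(X1 ≤ 1) = 0.867^15 + 15 × 0.133 × 0.867^14 = 0.388 (stated 38.8%).

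Probability of rejecting the null: the sum over x1 from the stage 1 minimum to 15 of P(X1 = x1) × P(X2 ≥ r − x1), with X1 and X2 independent Binomial(15, p) and r = 4 or 7.
- A: 0.0582 at p0 (stated 6%) and 0.800 at p1 (stated 80%).
- B: 0.0917 at p0 (stated 9.2%) and 0.801 at p1 (stated 80.1%).

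All stated figures reproduce, so the design calculations contain no error.

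**Step 3. Worst case: enrol straight to 30, with no stop at stage 1.** The rejection probability becomes P(X ≥ r) with X ~ Binomial(30, p). Expected N under the null with the stop is 15 + 15 × (1 − stopping probability):
- A: 15 + 15 × (1 − 0.463) = 23.1.
- B: 15 + 15 × (1 − 0.388) = 24.2.

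| | Cohort A, with stop | Cohort A, without | Cohort B, with stop | Cohort B, without |
|---|---|---|---|---|
| Early stopping under the null | 46.3% | 0% | 38.8% | 0% |
| Expected N under the null | 23.1 | 30 | 24.2 | 30 |
| Type I error | 5.8% | 6.1% | 9.2% | 9.4% |
| Power | 80.0% | 81.4% | 80.1% | 81.0% |

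The average excess under the null is 30 − 23.1 = 6.9 patients in Cohort A and 30 − 24.2 = 5.8 in Cohort B. Both type I errors stay below the 0.10 target.

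**The case against.** The strongest reply is that the run-in sentences are permissive and concern safety only. They say what clearing the DLT check allows; they do not waive the separate efficacy condition, and both can apply together. That stands. A reader might infer that the completion wording removes the Simon futility stop, or that the run-in text is the only instruction governing when enrolment continues. The documents support neither inference: the synopsis, Sections 5.2, 10.2 and 10.5, and SAP 2.2, 2.4 and 9.5 set or repeat the stage 1 decision independently of the run-in, and no passage cancels it.

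Two further replies have weight. First, Section 3.1.2 reports no DLTs among 11 patients enrolled by 29 October 2020, shortly before protocol version 4.0. The three one-DLT phrases may therefore never come into play, although the documents do not say that the run-in had formally closed. Second, the synopsis bullets name Cohort A only, so carrying the effect over to Cohort B is an inference. The one-DLT sentences name no cohort, which keeps that inference open but does not establish it.

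None of this reconciles the text. The no-DLT bullet in the synopsis still grants a wider permission than the paragraph above it, Section 5.2 and the SAP.

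**Conclusion.** Wrong as written, minor: an internal contradiction in an enrolment rule. The stage 2 gate remains in force on a reading of the whole protocol, but a site or the sponsor acting on the completion wording would bypass it.

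The figures without the stop are a worst case. They assume that the stage 1 decision is ignored altogether, that the null response rate holds, and that each cohort enrols exactly 30 evaluable patients. On those terms Cohort A loses its 46% chance of stopping early and enrols 6.9 more patients on average. The same calculation for Cohort B (38.8% to 0%, 5.8 more patients) also assumes that the wording reaches that cohort. There is no false-positive problem: type I error stays under 0.10 and power rises by about one percentage point. The loss is avoidable exposure, together with stopping probabilities that would not describe the trial.

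**What to change.** Reconcile the four completion phrases (the one-DLT sentence and both bullets in the synopsis, and the one-DLT sentence in Section 5.2) with Section 10.2 and SAP 2.2. The common wording should say that clearing the run-in opens enrolment only as far as the 15 evaluable stage 1 patients of a cohort, and that stage 2 enrolment opens only once that cohort has met its stage 1 response criterion in Section 10.2. Leave the DLT criteria unchanged. The SAP bullets already carry the stage 1 limit and need no edit.

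The cost is four phrases in the protocol. No threshold or sample size changes. The downside is a possible short accrual pause at the stage 1 look, which the stated 46% and 38.8% already presuppose.
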